- Mortality and adverse events of special interest over 1 year (52 weeks).
- Corticosteroid reduction during Weeks 40-52.

Diagnosis & Inclusion Criteria: Subjects enrolled in the study must meet the following inclusion criteria:

1. Males or females ≥ 18 years.
2. Have a diagnosis of SLE, refer to ACR revised criteria for the classification of SLE ([Appendix 1](#)) as a guide for diagnosis of SLE.
3. Active, autoantibody positive SLE (autoantibody positive is defined as the presence of ANA or anti-dsDNA antibodies).
4. Are on a SLE treatment regimen consisting of any of the following medications (alone or in combination):
 - Corticosteroids
 - Other immunomodulatory agents including methotrexate, azathioprine, leflunomide, mycophenolate (including mycophenolate mofetil, mycophenolate mofetil hydrochloride, and mycophenolate sodium), calcineurin inhibitors (eg, tacrolimus, cyclosporine), sirolimus, oral cyclophosphamide, 6-mercaptopurine, or thalidomide.
 - Anti-malarials [eg, hydroxychloroquine, chloroquine, quinacrine (mepacrine)]
5. A female subject is eligible to enter the study if she is:
 - Not pregnant or nursing;
 - Of non-childbearing potential defined as:
 - pre-menopausal females with a documented tubal ligation, hysterectomy, documented hysteroscopic tubal occlusion procedure with follow-up confirmation of bilateral tubal occlusion, or documented bilateral oophorectomy or
 - postmenopausal defined as 12 months of spontaneous amenorrhea with an appropriate clinical profile [e.g., > 45 years, in the absence of hormone replacement therapy or other cause for amenorrhea]; in questionable cases obtain a blood sample for follicle stimulating hormone (FSH) and estradiol simultaneously to confirm. Diagnostic levels for FSH and estradiol vary by specific laboratories/assays;

- OR is of child-bearing potential with negative pregnancy test as determined by urine human chorionic gonadotrophin (hCG) test at screening and urine hCG test prior to dosing AND
 - Agrees to use one of the contraception methods listed in the protocol (see Section 4.3) for 2 weeks prior to the day of dosing to sufficiently minimize the risk of pregnancy at that point. Female subjects must agree to use contraception until 16 weeks following the last dose of study agent.
 - OR has only same-sex partners, when this is her preferred and usual lifestyle.
6. Have the ability to understand the requirements of the study, provide written informed consent (including consent for the use and disclosure of research-related health information), and comply with the study data collection procedures [including annual contacts from Years 2 through 5 (Week 260) to assess mortality and malignancy].

Exclusion Criteria: Subjects will be excluded from participating in the study if they meet any of the following exclusion criteria:

1. Have received any prior treatment with belimumab, either as a marketed product or as an investigational agent.
2. Have received treatment with B cell targeted therapy (eg, rituximab, other anti-CD20 agents, anti-CD22 [epratuzumab], anti-CD52 [alemtuzumab], BLyS-receptor fusion protein [BR3], TACI-Fc, anti-BAFF [LY2127399]) within 364 days of Day 0.
3. Have received any of the following within 90 days of Day 0:
 - Any biologic agent (eg, adalimumab, etanercept, infliximab, anakinra) other than B cell targeted therapy (see Exclusion Criterion 2).
 - Plasmapheresis.
4. Have received any of the following within 60 days of Day 0:
 - A non-biologic investigational agent.
5. Have received any of the following within 30 days of Day 0:
 - A live vaccine.
6. Have a history of malignant neoplasm within the last 5 years, except for adequately treated cancers of the skin (basal or squamous cell) or carcinoma in situ of the uterine cervix.
7. Have required management of acute or chronic infections, as follows:
 - Currently on any suppressive therapy for a chronic infection (such as tuberculosis, pneumocystis, cytomegalovirus, herpes simplex virus, herpes zoster and atypical mycobacteria).
 - Hospitalization for treatment of infection within 60 days of Day 0.
 - Use of parenteral (IV or IM) antibiotics (antibacterials, antivirals, anti-fungals, or anti-parasitic agents) within 60 days of Day 0.
8. Have severe lupus kidney disease (defined by proteinuria > 6 g/24 hour or equivalent using spot urine protein to creatinine ratio, or serum creatinine > 2.5 mg/dL), or have severe active nephritis requiring acute therapy, or have required hemodialysis or high-dose prednisone or equivalent (> 100 mg/day) within 90 days of Day 0.

9. Have severe active central nervous system (CNS) lupus (including seizures, psychosis, organic brain syndrome, cerebrovascular accident [CVA], cerebritis or CNS vasculitis) requiring therapeutic intervention.
10. Known HIV infection.
11. Current or history of hepatitis B or hepatitis C infection.
12. **Only applicable to Lithuanian sites:**
 - Have hypogammaglobulinaemia (IgG <400 mg/dL) or a deficiency in immunoglobulin A (IgA <10 mg/dL).
 - Have had renal, stem cell/marrow or other major organ transplant.
 - Have a chronic infection or a history of recurrent infections, which in the opinion of the investigator poses a significant risk to the subject.
 - Have received cyclophosphamide via any route of administration within 90 days of Day 0.

Study Design and Schedule:

This is a global, multi-center, randomized, placebo-controlled study to evaluate adverse events of special interest in adults with active, autoantibody-positive systemic lupus erythematosus (SLE) treated with belimumab plus standard therapy vs placebo plus standard therapy. It was initially planned that approximately 5,000 subjects would be randomized to 1 of 2 treatment groups: belimumab 10 mg/kg (2,500 subjects) or placebo (2,500 subjects) plus standard therapies. Subsequent to the completion of 2 additional placebo-controlled trials, it was estimated based on data from all 5 of the completed Phase 2/3 trials that adverse event rates could be assessed with the same planned level of precision with a total sample size of 4,000 subjects. Consequently, a sample size reduction was proposed to and accepted by the FDA and EMA regulatory authorities.

Subjects will receive study agent (belimumab or placebo) on Days 0, 14, 28 and approximately every 28 days thereafter through Week 48 with a final visit conducted at Week 52. Subjects who discontinue treatment at any time during the 52-week study will be followed for mortality and malignancy including non-melanoma skin cancers (NMSC) at 1 year (through Week 52) and annually for Years 2 through 5.

Subject data will be collected at randomization and subsequently at approximately 28-day intervals for 52 weeks. Subjects will be assessed for malignancies including NMSC, serious infections, opportunistic infections and other infections of interest, selected serious psychiatric events, suicidality, and serious infusion and hypersensitivity reactions. All cause mortality will be reported. All other serious adverse events (SAEs), irrespective of causality, will also be recorded. Medical history will be collected on all subjects. Immunomodulatory agents used to treat SLE at baseline and during study, hospitalizations, and organ damage (SLICC/ACR Damage Index) will also be assessed through Week 52.

All subjects will have a follow-up visit performed approximately 4 weeks after the last dose of study agent. In the event that a subject withdraws consent to participate in the first year monthly study visits, an attempt should be made at the time of consent withdrawal to obtain consent to contact the subject at Week 52 and annually for Years 2 through 5 (Week 260) to assess mortality and malignancy (including NMSC).

Subjects may continue to receive their other SLE medications including corticosteroids, immunomodulatory agents and antimalarials; changes in these SLE medications during the trial will be permitted as clinically indicated. No concomitant biological therapies will be allowed during the 52-week study. In the event that the treating physician decides that a subject requires the addition of a biologic agent before Week 52, the subject is withdrawn from study agent treatment, but is followed on the study through Week 52 and annually for Years 2 through 5 (Week 260).

Following the 52-week study, all subjects will be contacted annually through Year 5 (Week 260) to assess mortality and malignancy (including NMSC).

At the end of the 52-week study, subjects who wish to continue treatment may be able to do so by being prescribed commercially available belimumab. If belimumab is not commercially available in a subject's country of participation, the subject may be able to receive belimumab under a separate continuation protocol. A separate informed consent will need to be provided for the continuation protocol.

An Independent Data Monitoring Committee (IDMC) will review unblinded safety data for this study on an ongoing basis until the data are locked and analyzed. The IDMC will include at least 3 physicians, and a statistician, none of whom are affiliated with the sponsor. The first IDMC meeting will review the data after approximately 500 subjects have been treated or 6 months from randomization of the first patient, whichever is first. After the initial review, the IDMC will continue to review the data approximately every 6 months. Events to be monitored during the safety review will include at a minimum all serious adverse events (including deaths, serious psychiatric events and serious infections), opportunistic infections (serious and nonserious) and other infections of interest, malignancies (including NMSC), and serious infusion and hypersensitivity reactions. Investigators and IRBs/IECs will be notified of the outcome of each IDMC meeting.

Endpoints and Statistical Analysis:

The main purpose of this study is to provide an evaluation of the difference in the rates of all prespecified AESI and all cause mortality between the belimumab and the placebo groups with a 2-sided 95% confidence interval (CI). SAEs will be analyzed descriptively only.

Safety Endpoints:

The table below describes the safety endpoints and measures collected in the study.

All-cause mortality
Serious Infections (including serious opportunistic infections and any event of TB or TB reactivation)
Non-serious opportunistic infections and other infections of interest (Appendix 2)
Malignancies (excluding NMSC)
Non-melanoma skin cancers
Psychiatric events suggesting serious mood disorders and anxiety
Suicidality (using C-SSRS; Appendix 4 and Appendix 5)
Serious Infusion and Hypersensitivity Reactions
All SAEs

Efficacy Endpoints:

The major efficacy endpoint is:

- Percent of subjects whose average prednisone (or equivalent) dose has been reduced by $\geq 25\%$ from baseline to ≤ 7.5 mg/day during Weeks 40 through 52 (in the subgroup of subjects receiving > 7.5 mg/day of prednisone (or equivalent) at baseline).

Other efficacy endpoints include:

- Use of immunomodulatory medications to treat SLE over 1 year.
- Number of hospitalizations per patient.
- Percent of patients hospitalized.

SLICC/ACR Damage Index will be recorded at baseline and at Week 52 to allow assessment of accrual of damage in subjects who may be followed in a subsequent study.

Sample Size Considerations:

The sample size is based on the feasibility of enrolling a large number of SLE subjects in a global trial that will provide a reasonable estimate for mortality and other AESI rates. Originally, the sample size was approximated at 5,000 subjects to be randomized (1:1 randomization; 2,500 per treatment group) to thereby allowing the difference in mortality rate between the belimumab- and placebo-treated groups to be established with a 95% CI of $\pm 0.46\%$ (see Section 8.4 of the protocol).

Following completion of two additional placebo-controlled trials (each comprising 1 year of treatment), a revised mortality estimate based on data from all 5 of the completed 2/3 trials enabled the same level of precision (i.e., a 95% CI of $\pm 0.46\%$) for the difference in mortality between placebo and belimumab to be achieved with 4,000 subjects.

Consequently, a proposal to reduce the sample size from 5,000 to 4,000 subjects was accepted by regulatory authorities.

The randomization will be stratified for region (US/Canada vs Central America/South America/Mexico vs Europe/Australia/Israel vs Asia), SELENA SLEDAI score (≤ 9 vs ≥ 10), and steroid dose (≤ 7.5 mg/day vs >7.5 mg/day prednisone or equivalent).

Safety Analysis:

Mortality and AESI will be summarized descriptively using number and percentage of subjects and will be analyzed using an estimation paradigm. The difference in the rates of all prespecified AESI and all cause mortality, between the belimumab and the placebo groups will be evaluated with a 2-sided 95% CI. SAEs will be analyzed descriptively only. Deaths will also be described in detail, including, in the belimumab group, assessment of relationship to belimumab treatment. The frequency and rate of serious adverse events will be tabulated by MedDRA system organ class (SOC) and preferred term. The SAE rates may also be reported adjusted for subject years.

For all cause mortality, the hazard ratio (and its 95% CI) for belimumab vs placebo will be estimated using the Cox proportional hazard model, adjusted for baseline randomization factors. The time to death will be censored at the last follow-up by the end of the study for subjects who are alive.

Safety analyses will be performed using the As-Treated population, defined as all randomized subjects who receive a dose of study agent, grouped according to the actual treatment administered to the subject for more than 50% of the doses.

Analysis of Major Efficacy Endpoint:

The percent of subjects with average prednisone (or equivalent) dose that has been reduced by $\geq 25\%$ from baseline to ≤ 7.5 mg/day during Weeks 40 through 52 will be compared between the belimumab and the placebo groups using a logistic regression model, adjusted for baseline prednisone (or equivalent) dose level, baseline SELENA SLEDAI score (≤ 9 vs ≥ 10), and region (US/Canada or Central America/South America/Mexico or Europe/Australia/Israel or Asia). The analysis will be performed on subjects who were using prednisone (or equivalent) at a dose > 7.5 mg/day at baseline and were in the intent-to-treat (ITT) population. In the analysis, all subjects who drop out and/or add new immunosuppressive agents before the Week 52 visit will be considered having no steroid reduction. However, switching immunomodulatory agents for toxicity reasons or lack of availability (eg, no longer manufactured or no longer reimbursed) is permitted and will not be imputed as no steroid reduction. To examine the robustness of the results, a sensitivity analysis of the steroid reduction may be performed without considering any information related to the use of new immunomodulatory agents.

Study Calendar:

See Section 6 for a calendar of study visits and assessments.

Table of Contents

Study Synopsis.....	4
Table of Contents.....	10
List of Tables	12
List of Abbreviations	13
1 Background.....	15
1.1 Disease Background Relevant to Clinical Study	15
1.2 Study Agent Background Relevant to Clinical Study.....	17
1.3 Rationale for the Study	19
1.4 Benefit-Risk Assessment	20
1.4.1 Risk Assessment	20
1.4.2 Benefit Assessment.....	25
1.4.3 Overall Benefit:Risk Conclusion	25
2 Study Objectives	25
3 Study Design.....	25
3.1 Basic Design Characteristics.....	25
4 Inclusion and Exclusion Criteria.....	27
4.1 Inclusion Criteria	27
4.2 Exclusion Criteria	28
4.3 Contraception Requirements for Female Subjects.....	29
5 Study Treatment Regimen	30
5.1 Study Agent Name and Formulation	30
5.2 Packaging, Labeling, Preparation, and Storage	30
5.3 Dose, Route of Administration, and Schedule.....	31
5.4 Alteration of Dose/Schedule Due to Toxicity.....	32
5.5 Concurrent Medications.....	32
5.5.1 Prohibited Medications	32
5.5.2 Allowable Medications	33
6 Study Procedures	33
6.1 Screening Procedures (Day -30 to Day 0)	33
6.2 Study Enrollment Procedures	34
6.3 Treatment Period.....	34
6.4 Post-Treatment Follow-Up	34
6.5 Discontinuation of Study Agent.....	34
6.6 Withdrawal from Study.....	35

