n/N%	0.4%	0.8%	0.7%	0.5%	0.4%	0%

n=number of subjects

Likewise, rates of adverse events of special interest (AESIs), including malignancy, infection and psychiatric events are summarized in Table 1-2 for data generated in IV and SC controlled, repeat dose belimumab studies.

Table 1-2 AESIs in Belimumab IV and SC SLE Controlled Repeat Dose Studies

	C1056/C1057/LBSL02 Pooled IV		BEL112341 SC		BEL113750 IV	
	Pbo N=675	Bel N=1458	Pbo N=28 0	Bel N=556	Pbo N=23 5	Bel N=470
Malignancies including NMSC						
n	2	5	1	2	0	1
n/N%	0.3%	0.3%	0.4%	0.4%	0%	0.2%
Malignancies excluding NMSC						
n	1	2	1	2	0	1
n/N%	0.1%	0.1%	0.4%	0.4%	0%	0.2%
Serious Infections of Special Interest						
n	5	19	3	8	7	11
n/N%	0.7%	1.3%	1.1%	1.4%	3.0%	2.3%
Opportunistic Infections						
n	8	15	1	2	5	13
n/N%	1.2%	1.0%	0.4%	0.4%	2.1%	2.8%
Depression/Suicide/Self Injury						
n	56	146	10	17	6	10
n/N%	8.3%	10.0%	3.6%	3.1%	2.6%	2.1%

Malignancies (excluding NMSC) assessed across all IV and SC SLE belimumab studies as of 08 March 2016, including safety data from double-blind and open-label studies/portions of studies and adjusted for patient-years exposure were compared with the malignancy rate in SLE patients reported in a large international cohort study of cancer in SLE ([Bernatsky et al, 2005](#)). Excluding NMSC, the malignancy rate per 100 patient-years with belimumab is 0.45 (95% CI 0.33, 0.59) compared with a background rate in SLE patients of 0.53 (95% CI 0.48, 0.59). Excluding NMSC is appropriate given that they are generally nonserious events with a high cure rate and it is known that NMSC is underreported in observational studies compared with prospective clinical trials ([Great Britain National Cancer Statistics, 2010](#); [Young et al, 2007](#)). No pattern of malignancies or increase in any particular type of malignancy was identified in patients receiving belimumab other than would be expected in an SLE population with a predominance of women.

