8.1 General Statistical Considerations

This main purpose of this study is to provide an evaluation of the difference in the rates of all prespecified AESI and all cause mortality between the belimumab and the placebo groups with a 2-sided 95% confidence interval (CI). SAEs will be analyzed descriptively only.

Safety analyses will be performed on the as-treated population defined as all subjects who are randomized and received at least 1 dose of study agent, grouped according to the treatment that was received for >50% of doses. Secondary efficacy endpoints will be analyzed using the ITT population, grouped according to the treatment that a subject was randomized to receive, regardless of the actual treatment received.

The final analysis for the 52-week study will be performed when all the data have been collected, verified and validated for all subjects through the Week 52 visit.

An interim analysis will be conducted once at least 2000 randomized subjects have completed through Week 52. The interim analysis is solely for monitoring patients' safety and reporting event rates to health authorities. It will be descriptive in nature and no comparative statistical inferences for claims will be made. Therefore, there will be no adjustment to Type I error for the interim or the final analyses. To minimize bias and to maintain data integrity, the interim analysis will be performed by a statistician who is not affiliated with the study conduct. Similarly, sponsor staff who have access to the interim results will not be involved in subject level monitoring of the study. Site personnel, investigators, and subjects will remain blinded until the study is complete and the final results are made public.

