8.4 Sample Size Rationale

It was originally planned that a target of 5,000 SLE subjects would be enrolled in this safety study. The sample size was based on the feasibility of enrolling a large number of SLE subjects in a global trial that would provide a reasonable estimate for mortality and other AESI rates. The study design was designed to allow the difference in mortality rates between the placebo and the belimumab treated groups to be established with a 95% confidence interval (CI) of $\pm 0.46\%$ (ie, within -0.46% and 0.46%), assuming the estimated first year mortality rate was the same 0.68% in the 2 treatment groups. The estimated reference AE mortality rates were based on the annual AE mortality rates in the pooled primary safety database in SLE subjects (integrated database of LBSL02 [placebo-controlled treatment phase only], HGS1006-C1056, and HGS1006-C1057).

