8.4.1 Sample Size Re-Estimation

Following the completion of 2 additional placebo-controlled trials (BEL112341/C1115, BEL113750), revised mortality estimates based on data from all 5 of the completed studies were as follows: 0.504% (6/1,190 for the placebo group) and 0.564% (14/2,484 for the belimumab group) with a delta of 0.060% .

Using a conservative revised mortality rate of 0.564% , the 95% CI for a 4,000 subject sample size with 1:1 randomization was also $\pm 0.46\%$. As a result, given the revised mortality estimate, a sample size of 4,000 subjects would not result in any loss of precision (i.e., the width of the 95% CI remains unchanged). Therefore, agreement was reached with regulatory authorities to reduce the sample size from 5,000 to 4,000 subjects.

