5. SAMPLE SIZE CONSIDERATIONS

5.1. Sample Size Assumptions

It was originally planned that a target of 5,000 SLE subjects would be enrolled in this safety study. The sample size was based on the feasibility of enrolling a large number of SLE subjects in a global trial that would provide a reasonable estimate for mortality and other AESI rates. Assuming a common first year mortality rate of 0.68% for both treatment groups, the precision of the 95% CI for the difference between treatment groups is $\pm 0.46\%$.

Following the completion of 2 additional placebo-controlled trials (BEL112341/C1115, BEL113750), revised mortality estimates based on data from all 5 of the completed studies were as follows: 0.504% (6/1,190 for the placebo group) and 0.564% (14/2,484 for the belimumab group) with a delta of 0.060%.

Using a conservative revised mortality rate of 0.564%, the 95% CI for a 4,000-subject sample size with 1:1 randomization was also $\pm 0.46\%$. As a result, given the revised mortality estimate, a sample size of 4,000 subjects would not result in any loss of precision (i.e., the width of the 95% CI remains unchanged). Therefore, agreement was reached with regulatory authorities to reduce the sample size from 5,000 to 4,000 subjects.

All sample size calculations were performed using the Chi-Square Simple Asymptotic Pearson method in Power Analysis and Sample Size software (PASS 2012).

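### Does the synopsis wrongly claim that cutting the sample to 4,000 keeps the planned precision for adverse event rates in general?

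*Protocol*

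**What the plan says.** The synopsis, under Study Design and Schedule, recalls the original plan for 5,000 subjects. It then says that "adverse event rates could be assessed with the same planned level of precision with a total sample size of 4,000 subjects", citing the five completed Phase 2/3 trials, and presents the reduction accepted by the FDA and EMA as the consequence.

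Four other places give the reasoning behind the sample size:

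- Synopsis, Sample Size Considerations: the ±0.46% interval is said "for the difference in mortality between placebo and belimumab to be achieved with 4,000 subjects".
- Protocol section 8.4: the half-width of ±0.46% is for the mortality difference, at 0.68% in each arm. Beyond that, it says only that a large global trial "would provide a reasonable estimate for mortality and other AESI rates".
- Protocol section 8.4.1: "given the revised mortality estimate, a sample size of 4,000 subjects would not result in any loss of precision".
- Week 52 SAP, section 5.1: the same calculation, which begins "Assuming a common first year mortality rate of 0.68% for both treatment groups" and names the simple asymptotic (Pearson) method.

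Protocol section 3.1 reports the reduction and makes no claim about precision. The stated main purpose of the study is an "evaluation of the difference in the rates of all prespecified AESI and all cause mortality between the belimumab and the placebo groups", each with a two-sided 95% interval. No planning rate or half-width is given for any AESI at either sample size.

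**The concern.** The synopsis sentence is the stated reason for a 20% cut in sample size, and its wording takes in adverse events generally. The calculation behind it covers mortality only, and it works because the assumed death rate was lowered at the same time as the sample. Nothing shows a matching fall for infections, malignancies, psychiatric events or infusion reactions. Because the AESI differences share the main purpose with mortality, a reader who stopped at this sentence could credit those comparisons with a retained precision that was never demonstrated.

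**Working it through.** **Inputs.** Two-sided 95% level, z = 1.96. Original plan: p = 0.68%, n = 2,500 per arm (protocol 8.4). Revised plan: p = 0.564%, n = 2,000 per arm (protocol 8.4.1). Equal rates in both arms.

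**Formula.** Half-width = 1.96 × √(2p(1−p)/n).

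**Reproducing the plan's figure.**

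- Original: 1.96 × √(2 × 0.0068 × 0.9932 / 2,500) = 0.456%.
- Revised: 1.96 × √(2 × 0.00564 × 0.99436 / 2,000) = 0.464%.
- Both round to ±0.46%, as stated. The revised interval is 0.4642/0.4556 = 1.019 times the original. With the pooled five-study rate, 20/3,674 = 0.544%, it is 0.456%, the same as the original.

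**What the lower rate contributes.** At an unchanged 0.68% with 2,000 per arm the half-width is 0.509%. For any event with an unchanged rate the factor is √(2,500/2,000) = 1.118. To keep the width exactly, p(1−p) must fall to 2,000/2,500 = 0.8 of its former value; for mortality that means 0.68% falling to 0.543%.

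**Illustration for AESIs.** The rates below are assumptions, since the documents plan none.

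| Assumed common rate | 5,000 subjects | 4,000 subjects |
|---|---|---|
| 1% | ±0.55% | ±0.62% |
| 5% | ±1.21% | ±1.35% |
| 10% | ±1.66% | ±1.86% |

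**Can Table 1-2 settle it?** Protocol section 1.2 says "rates of adverse events of special interest (AESIs), including malignancy, infection and psychiatric events are summarized in Table 1-2", so one can compare the three-study pool (675 + 1,458 = 2,133 subjects) with all five studies (3,674). Serious infections of special interest go from 24/2,133 = 1.13% to 53/3,674 = 1.44%, and opportunistic infections from 23/2,133 = 1.08% to 44/3,674 = 1.20%. Depression/suicide/self-injury falls from 202/2,133 = 9.47% to 245/3,674 = 6.67%. These shifts are weak evidence about the trial's endpoints, for three reasons:

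- Most rows are not the endpoints. SAP section 9.5.12 defines serious infections as all serious events in the infections system organ class, for which Table 1-3 cites 5%, and limits the psychiatric endpoint to serious events. The row that matches best, malignancies excluding non-melanoma skin cancer, has 3 events in three studies and 7 in five, and the 3 are among the 7.
- One added trial, in North East Asia (BEL113750), drives the infection rows. It has 7 + 11 = 18 of the 53 serious infections and 5 + 13 = 18 of the 44 opportunistic infections, in 235 + 470 = 705 subjects. Without it, 2,969 subjects remain: 53 − 18 = 35 serious infections (35/2,969 = 1.18%) and 44 − 18 = 26 opportunistic infections (26/2,969 = 0.88%). The first is then almost unchanged from the three-study rate and the second is lower.
- Exposure differs. C1056 ran for up to 76 weeks, and each of the two added trials had one year of treatment.

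So the table neither supports the broad claim nor measures how far it is off.

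**Which precision was planned?** The sentence speaks of the planned level of precision. The documents contain one such level, ±0.46% for the mortality difference. Section 8.4 calls its reference inputs AE mortality rates, which is a likely source of the shortened phrase. The Sample Size Considerations paragraph of the same synopsis repeats the argument (five trials, same precision, 4,000 subjects, regulatory acceptance), this time with the figure and the right scope.

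**The case for a change.** The strongest case for a change is that the phrase carries the justification for a smaller trial. The paragraph it sits in opens by describing a study of AESIs, so AESIs are its natural reading. Narrower statements elsewhere do not tell the reader that AESI precision was not examined. Replacing a few words would also cost almost nothing.

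Two parts of this stand. The sentence is literally wider than the calculation, and at unchanged rates the AESI intervals would be about 12% wider with 4,000 subjects than with 5,000.

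The rest does not carry. AESI precision was never set as a target at 5,000, so nothing planned was lost; the documents promised only reasonable estimates, tied to feasibility. A strict rule that the rate must fall by the full 20% would also be harder on AESIs than on mortality, where the assumed rate fell by (0.68 − 0.564)/0.68 = 17% and the match holds to two decimals.

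**Conclusion.** A clerical looseness in one narrative sentence, with no change needed. The mortality figure of ±0.46% is correct at both sample sizes, and the scope is stated correctly in the same synopsis, in protocol section 8.4.1 and in SAP section 5.1. The sample size, endpoints, analyses and reported intervals would be the same whichever way the sentence was worded. There is no formal hypothesis for the primary safety endpoints (SAP section 2.3), and each AESI difference will be reported with its observed 95% interval, so readers will see the precision achieved.

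The arithmetic assumes equal rates in the two arms, full enrolment of 2,000 or 2,500 per arm, and the simple asymptotic interval that the SAP names. The reading of the sentence rests on the documents containing no planned precision for any endpoint other than mortality.
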